#### **3.4.1.8 Rate of hospitalization due to COPD exacerbations per patient per year**

For the production of summary statistics, the rate of hospitalization due to COPD exacerbation per patient per year is calculated by applying the following in the general formula defined in Section 3.1.7.1.

- Event is hospitalization due to COPD exacerbation
- Period refers to the whole study period

#### **3.4.1.9 Number of days hospitalized due to COPD exacerbations**

The number of days hospitalized due to COPD exacerbations is calculated as follows:

*Number of days hospitalized due to COPD exacerbations = Sum of duration for all hospitalizations due to COPD exacerbations*

where

*Duration for each hospitalization due to COPD exacerbations = end date – onset date + 1*

Hospitalizations during the whole study period are counted in the calculation.

#### **3.4.1.10 Time to first hospitalization due to COPD exacerbations**

Time (in days) to first hospitalization due to COPD exacerbations is calculated by applying the following in the general formula defined in Section 3.1.7.3.

- Event is hospitalization due to COPD exacerbation
- Period refers to the whole study period

For patients who do not experience a hospitalization during the study, date of first hospitalization due to COPD exacerbation will be censored at the last dose date (or study closure date for patients who did not discontinue from study treatment). For patients who experience a hospitalization due to reasons other than COPD exacerbation during the study, patients will be censored at the date of first hospitalization (due to reasons other than COPD exacerbation).

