## 1.2 Study design

This is a Phase IV, multicenter, randomized, double-blind, placebo-controlled, parallel-group study evaluating the effect of Acclidinium Bromide (a long-acting muscarinic antagonist delivered by the Pressair® dry powder inhalation [DPI] device) compared with placebo on long-term CV safety and COPD exacerbations in outpatients at least 40 years of age who have been diagnosed with moderate to very severe COPD (postbronchodilator % predicted forced expiratory volume in 1 second [FEV1] < 80% and FEV1/forced vital capacity [FVC] ratio < 70%) and a history of CV or cerebrovascular disease and/or significant CV risk factors.

Note: in this document

1. The term “double-blind treatment period” applies to the following 2 scenarios:
  - When used in “maximum of 36-months double-blind treatment period”
  - When used for patients who completed 36-months treatment (completer)
2. The term “during the treatment period” refers to on-treatment period.
3. The term “during the whole study period” refers to both on-treatment and off-treatment (post-treatment follow-up) periods.

The study consists of two-week washout/run-in period (for patients on a long-acting muscarinic antagonist [LAMA]) followed by a maximum of 36-month double-blind treatment period.

Signed informed consent form (ICF) from the patient or the patient’s legally authorized representative will be obtained before any study-related procedures are begun. All patients will be assigned a patient identification (PID) number via the interactive web response system (IWRS). Patients meeting the entry criteria for this study will be randomized (1:1) to acclidinium bromide 400 µg (abbreviated as acclidinium hereafter) twice a day (BID) or placebo BID. This study will conclude when 122 patients have experienced an adjudicated MACE.

Patients who prematurely discontinue investigational product (IP) will participate in a post-treatment follow-up period. The follow-up period will include on-site visits and telephone visits to collect MACE, COPD exacerbations, concomitant medications, and SAEs for the remainder of the study duration.

An independent Data Safety Monitoring Board (DSMB) will be established for this study. The DSMB will periodically monitor and review relevant clinical safety data, including adjudicated MACE.

Patients will be assessed according to the Schedule of Evaluations (See Section 2 of the clinical study protocol [CSP]).

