#### **3.1.2 Censoring rules in time-to-event analyses**

In time-to-event analyses, patients who have not had the event(s) in question will be censored at the following time points as applicable, depending on whether it is an on-study or on-treatment analysis (see Section 4.1 for definitions):

For on-study analysis:

- The last visit (in this case the EOT visit) for patients who completed the treatment or patients who are still on treatment at the end of study date
- Last contact date for patients who pre-maturely discontinued IP and completed the study or patients who pre-maturely discontinued IP and are still in study at the end of study date
- Any patient who is lost to follow-up (LTFU) at the end of the study will be censored at the last study contact where all elements of the endpoint in question were assessed
- Patients who withdraw consent will be censored at date of withdrawal, except in the analysis of all-cause mortality as a single endpoint, when patients will be censored at the date of last known alive according to vital status data

For on-treatment analysis:

- Patients will be censored on the date of IP discontinuation

In analysis of time to CV death and composites including CV death, censoring will occur at date of death from non-CV causes. For endpoints not including death, all deaths are censoring events.

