#### **4.2.4.3 Additional efficacy variables**

Unless otherwise specified, the following variables will use data collected during the whole study period using on-treatment analysis.

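### SAP 3.4.1.10 counts first COPD hospitalizations over the whole study but censors patients without one at last dose; the two windows conflict and should be tied to the on-treatment default of 4.2.4.3

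*SAP*

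**What the plan says.** SAP section 3.4.1.10 defines the event window with the line "Period refers to the whole study period". Section 1.2 fixes that term: it "refers to both on-treatment and off-treatment (post-treatment follow-up) periods". The same section says that patients who stop IP early are followed by "on-site visits and telephone visits to collect MACE, COPD exacerbations, concomitant medications, and SAEs for the remainder of the study duration", so COPD hospitalizations after stopping are available to be counted.

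The censoring rule in 3.4.1.10 opens "For patients who do not experience a hospitalization during the study" and continues that the "date of first hospitalization due to COPD exacerbation will be censored at the last dose date". Patients who never stopped IP are censored at study closure instead. A first hospitalization for another reason is also a censoring event.

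Section 4.2.4.3 introduces the additional efficacy variables, this one among them, by saying that, unless otherwise specified, "the following variables will use data collected during the whole study period using on-treatment analysis". Section 4.1 leaves post-treatment follow-up events out of an on-treatment analysis, and section 3.1.2 censors on-treatment analyses at IP discontinuation. For on-study analyses, 3.1.2 uses a later date: "Last contact date for patients who pre-maturely discontinued IP and completed the study".

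**The concern.** Taken with the definition in section 1.2, section 3.4.1.10 gives events one window and censoring another. Consider two patients who stop IP at month 10 and stay in follow-up. One is hospitalized for COPD at month 20: this patient has an event during the study and enters at month 20. The other is never hospitalized and leaves the risk set at month 10. Whether time after stopping IP counts as time at risk then depends on the outcome.

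The SAP plans Kaplan-Meier curves, a Cox hazard ratio with confidence interval and p-value, and a log-rank test for this endpoint. If the rule is programmed literally, absolute hazards come out too high in both arms. The arm with more IP discontinuation also looks worse than it is, because it contributes more off-treatment events without the matching event-free time.

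**Working it through.** **Two readings of the text.** The SAP gives no figure for this endpoint, so there is none to reproduce. On the literal reading, 1.2 and 3.4.1.10 together count off-treatment events and censor at last dose. On the default reading, 4.2.4.3, 4.1 and 3.1.2 together exclude off-treatment events and censor at IP discontinuation. Only the second is coherent. The neighbouring first-exacerbation endpoint (3.4.1.6) uses the same whole-study wording but refers its censoring to 3.1.2, so events and censoring move together. The hospitalization endpoint has its own fixed rule and does not.

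**Inputs from the SAP.** 1:1 allocation, 4,000 patients, at most 36 months, 40% IP discontinuation and 20% study discontinuation at year 2, exponential times (1.2, 1.3.1).

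**Assumptions not in the SAP.** First-hospitalization rate λ, the split of IP discontinuation between arms, and how study exit relates to stopping IP.

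**Worked case, no drug effect, λ = 0.10 per year, half of those who stop IP leave the study at once.** Per patient, with τ = 3 years and δ = -ln(1 - 0.40)/2 = 0.2554 per year:

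- On-treatment time A = [1 - exp(-(λ+δ)τ)]/(λ+δ) = 1.845 years, giving λA = 0.1845 events.
- Off-treatment events B = ½[δA - exp(-λτ)(1 - exp(-δτ))] = ½[0.4712 - 0.7408 × 0.5352] = 0.0373. Their share of all events is 0.0373/0.2218 = 17%.
- Off-treatment time at risk is B/λ = 0.373 years. The literal rule drops the event-free part, ½ exp(-λτ)[τ - (1 - exp(-δτ))/δ] = 0.335 years, and keeps C = 0.038.
- Rate under the literal rule: 0.2218/(1.845 + 0.038) = 0.118 per year, against a true 0.100. This is about 18% too high, although both arms discontinue equally.

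The same formulas at 45% discontinuation on placebo (δ = 0.2989) and 35% on aclidinium (δ = 0.2154):

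- Placebo: (0.1749 + 0.0421)/(1.749 + 0.044) = 0.121.
- Aclidinium: (0.1940 + 0.0326)/(1.940 + 0.033) = 0.115.

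The rate ratio is about 0.949 when the truth is 1. A Cox fit to 2,000,000 simulated patients gives 0.945 (0.940 at λ = 0.05, 0.955 at λ = 0.2).

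**Simulated trials of 4,000, no true effect, λ from 0.08 to 0.15.** Cox hazard ratio and share of trials with p < 0.05 under the literal rule:

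| IP discontinuation at year 2, placebo/aclidinium | Study exits nested within IP stops (about 17% of events off treatment) | Study exit independent of IP stop (about 27% off treatment) |
|---|---|---|
| 40%/40% | about 1.00; about 5% | about 1.00; about 5% |
| 43%/37% | about 0.965; 8-9% | about 0.94-0.95; 13-19% |
| 45%/35% | about 0.94; 13-16% | about 0.91; 27-33% |

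Matched rules, either on-treatment throughout or on-study throughout, give about 1.00 and about 5% in every row.

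**With a true on-drug hazard ratio of 0.8** (λ = 0.10, nested exits, off-drug hazard as on placebo):

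| Discontinuation | Literal | On-study | On-treatment |
|---|---|---|---|
| 40%/40% | 0.836 | 0.838 | 0.806 |
| 45%/35% | 0.781 | 0.833 | 0.806 |

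The runs leave out the censoring at non-COPD hospitalization. Adding it at an assumed 0.15 per year (nested exits) lowers the false-positive rates to 6-7% at 43%/37% and 9-12% at 45%/35%.

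**The case against.** The best defence is that the rest of the SAP points to an on-treatment analysis. Section 4.2.4.1 lists on-treatment and on-study analyses, each over the whole study period. There the phrase marks only the time horizon, as opposed to the first year, and the choice of on-treatment or on-study is a separate matter. Section 4.2.4.3 pairs the terms in the same way. If the whole-study line in 3.4.1.10 overrode the default, the identical line elsewhere in 3.4.1 would do so too, and the default would apply to almost nothing. Last-dose censoring is itself a sign of on-treatment intent. On that reading no off-treatment event is counted and the bias does not arise.

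This stands as the likelier intent. It does not remove the conflict. Section 1.2 defines the term explicitly as including post-treatment follow-up, and 4.2.4.3 gives way where something else is specified. Section 3.4.1.10 identifies event-free patients by the study, not by the treatment period.

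Two further objections also stand. The SAP assumes a single 40% discontinuation rate, so the unequal splits are illustrations. And if 40% is meant to cover all cessation of IP, independent study exit overshoots it: 1 - 0.6 × 0.8 = 52% would be off drug at year 2. That makes the right-hand column of the simulation table the less natural scenario.

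**Conclusion.** The finding is an unresolved conflict between 3.4.1.10 (with 1.2) and 4.2.4.3 (with 4.1 and 3.1.2), which produces a flawed analysis if 3.4.1.10 is programmed as written. In that case absolute hazards and Kaplan-Meier curves are distorted whatever the discontinuation pattern, and the hazard ratio is biased in favour of the arm with less IP discontinuation. The sizes in the tables depend on assumed hospitalization rates, assumed arm splits and the study-exit structure. Unequal discontinuation is a live possibility, since section 4.2.1 plans a log-rank comparison of it, but the SAP gives no split.

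Three stronger readings are not supported. A reader might infer that the hazard ratio is biased in any event: with equal discontinuation and no drug effect it is not. A reader might take 0.91 and 27-33% as the expected size: those figures need a ten-point difference between arms together with study exit independent of stopping IP. And a reader might infer harm to the trial's main conclusions. This is an additional efficacy variable outside the sequential testing of section 4.2.4, with descriptive p-values, so the impact is limited. The use of study closure as the censoring date for patients who stay on IP is not a separate fault, since no harm from it is shown.

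**What to change.** In section 3.4.1.10, state that the endpoint follows the on-treatment default of 4.2.4.3. Only COPD hospitalizations up to IP discontinuation count. All other patients, including those first hospitalized in post-treatment follow-up, are censored at that date under the on-treatment rule of 3.1.2. Give the censoring at non-COPD hospitalization the same window. If an on-study version is also shown, count follow-up events there and use the on-study censoring dates of 3.1.2.

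The cost is a few lines of SAP text and one programming change. No new data are needed.

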#### **3.4.1.6 Time to COPD exacerbation**

- Time to first COPD exacerbation

Time to first COPD exacerbation is calculated by applying the following in the general formula defined in Section 3.1.7.3.

- Event is mild, moderate, or severe COPD exacerbation
- Period refers to the whole study period

For patients who do not experience a COPD exacerbation during the study, start date of the first COPD exacerbation will be censored per general censoring rules described in Section 3.1.2, i.e., the event in question refers to a COPD exacerbation.

- Time to first moderate or severe COPD exacerbation during the first year of treatment

Time to first moderate or severe COPD exacerbation during the first year of treatment is similarly calculated and censored as time to first COPD exacerbation, by considering moderate or severe COPD during the first year of treatment only, i.e., patients will be censored on the date of IP discontinuation or at the end of the first year, whichever is earlier.

- Time to first moderate or severe COPD exacerbation

Time to first moderate or severe COPD exacerbation is similarly calculated and censored as time to first COPD exacerbation, by considering moderate or severe COPD only.

- Time to second COPD exacerbation

Time to second COPD exacerbation is calculated as follows:

*Start Date of the second COPD exacerbation – Date of randomization + 1.*

Time to second COPD exacerbation will be analyzed in patients who experience at least one COPD exacerbation. For patients who experience < 2 COPD exacerbations during the study, start date of the second COPD exacerbation will be censored per general censoring rules described in Section 3.1.2, i.e., the event in question refers to the second COPD exacerbation.

- Time to second moderate or severe COPD exacerbation

Time to second moderate or severe COPD exacerbation is similarly calculated and censored as time to second COPD exacerbation, by considering moderate or severe COPD only.

- Time to third COPD exacerbation

Time to third COPD exacerbation is calculated as follows:

*Start Date of the third COPD exacerbation – Date of randomization + 1.*

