#### **3.4.1.7 Time to Withdrawal from the double-blind IP due to COPD exacerbation**

Time (in days) to withdrawal from the double-blind IP due to COPD exacerbation is calculated as follows:

*Date of withdrawal from the double-blind IP due to COPD exacerbation – Date of randomization + 1.*

- For patients who do not withdraw from the double-blind IP, date of withdrawal from the double-blind IP due to COPD exacerbation will be censored at the last dose date.
- For patients who withdraw from the double-blind IP due to reasons other than COPD exacerbation, patients will be censored at the date of withdrawal from the double-blind IP (due to reasons other than COPD exacerbation).

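### Section 3.4.1.10 censors time to first COPD hospitalization at the first non-COPD hospitalization, an admission that ends neither follow-up nor the risk of the event

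*SAP*

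**What the plan says.** Section 3.4.1.10 names the event as a hospitalization due to COPD exacerbation and gives two censoring sentences.

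- The first begins "For patients who do not experience a hospitalization during the study". It censors those patients at the last dose, or at study closure if they did not discontinue treatment.
- The second sets this rule: "patients who experience a hospitalization due to reasons other than COPD exacerbation during the study, patients will be censored at the date of first hospitalization".

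The general rules in Section 3.1.2 apply to patients who have not had the event in question. For the on-treatment analysis they state: "Patients will be censored on the date of IP discontinuation". They also state: "For endpoints not including death, all deaths are censoring events". They do not mention hospitalization for another cause.

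Section 4.2.4.3 puts this endpoint on an on-treatment basis and plans Kaplan-Meier curves, a log-rank test and a Cox model with a hazard ratio, confidence interval and p-value.

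**The concern.** Censoring is appropriate where observation stops or the event can no longer occur. A non-fatal admission for another cause does neither. Section 1.2 keeps even patients who stop treatment under follow-up for COPD exacerbations and SAEs.

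The rule also leaves two programmers free to build different data sets. One would stop the clock at the non-COPD admission for everybody and lose any later COPD admission. The other would stop it only for patients who never have a COPD admission, and would thereby use the future to decide who leaves the risk set. Neither estimates the risk of a first COPD hospitalization cleanly, and the two err in opposite directions when the two admission risks are positively correlated.

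**Working it through.** **Comparison within the SAP**

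- Section 3.4.1.6, time to first exacerbation: "start date of the first COPD exacerbation will be censored per general censoring rules described in Section 3.1.2". It adds no censoring at another type of event.
- Sections 3.4.1.8 and 3.4.1.9: a COPD admission after a non-COPD admission counts in the hospitalization rate and in days hospitalized. Under the literal reading it is absent from time to first COPD hospitalization.
- Section 3.5.1.2: an MI that follows a stroke still counts in the separate time-to-MI analysis. An earlier, different non-fatal event does not censor there.
- Section 3.4.1.7 has a similar sentence: "patients will be censored at the date of withdrawal from the double-blind IP (due to reasons other than COPD exacerbation". It is sound there, because a patient who has left treatment for another reason can no longer leave it because of an exacerbation. That logic does not carry over to hospitalization.

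**Inputs**

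The SAP states no event count, rate or power for this endpoint, so there is no figure to reproduce.

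- From the SAP: 4,000 patients and 40% treatment discontinuation at year 2, exponential (1.3.1); maximum follow-up of about 36 months (3.4.1).
- Assumed: COPD admission rate a = 0.10 per year; non-COPD admission rate b = 0.05, 0.10, 0.20 or 0.30 per year.
- Discontinuation hazard c = -ln(0.6)/2 = 0.2554 per year.

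**Literal reading, independent risks**

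P(event observed) = a/H × (1 - exp(-3H)).

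- Without the rule, H = 0.10 + 0.2554 = 0.3554, P = 0.1845, and 4,000 × P = 738 events.
- With the rule and b = 0.30, H = 0.6554, P = 0.1312, giving 525 events. The loss is 1 - 525/738 = 29%.

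The Kaplan-Meier risk at 3 years stays at 1 - exp(-0.30) = 0.259, because the censoring is then non-informative.

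**Restricted reading, independent risks**

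Let q(t) be the chance that a patient at risk at time t will still have an observed COPD admission: q(t) = a/(a+c) × (1 - exp(-(a+c)(3-t))). Patients with a past non-COPD admission stay in the risk set only if they will have the event, so the apparent hazard is a / [q(t) + (1 - q(t)) exp(-bt)].

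For b = 0.30 this is 0.100 at t = 0, 0.147 at t = 1.5 (q = 0.116) and 0.246 at t = 3. Simpson's rule gives a cumulative hazard of 0.5 × (0.100 + 4 × 0.147 + 0.246) = 0.467, so the apparent risk is 1 - exp(-0.467) = 0.373. Simulation with 1,000,000 patients gives 0.372.

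**Positively correlated risks**

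A shared gamma frailty was simulated. Its variance of 0.67 is an assumption, borrowed from the overdispersion factor that Section 1.3.2 uses for exacerbations.

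| Non-COPD rate per year | Events kept, literal (independent) | Lost | 3-year KM, independent: literal / restricted | 3-year KM, frailty 0.67: literal / restricted |
|---|---|---|---|---|
| rule not applied | 738 | 0 | 0.259 | 0.239 |
| 0.05 | 694 | 44 (6%) | 0.259 / 0.275 | 0.231 / 0.251 |
| 0.10 | 654 | 84 (11%) | 0.259 / 0.292 | 0.222 / 0.262 |
| 0.20 | 584 | 154 (21%) | 0.259 / 0.330 | 0.210 / 0.287 |
| 0.30 | 525 | 213 (29%) | 0.259 / 0.372 | 0.197 / 0.310 |

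With the frailty, the literal reading loses 8%, 15%, 26% and 35% of events at the four rates.

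**Hazard ratio**

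Assume a true value of 0.86.

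- If treatment does not affect non-COPD admissions, both readings move the estimate by less than 0.01.
- If treatment changes them by 10%, at a rate of 0.30, the literal reading moves it by at most 0.002 (independent) or about 0.017 (frailty), and the restricted reading by up to about 0.03.
- Under the literal reading with independent risks, the standard error of the log hazard ratio rises from 0.076 to 0.081-0.091 for non-COPD rates of 0.10 to 0.30.

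**The case against.** **The literal reading may not be the intended one.** Section 3.1.2 opens by limiting censoring to patients without the event. On that basis the rule touches only patients who never have a COPD hospitalization, and no event is discarded. This is a fair reading, and it means the 6% to 29% loss cannot be presented as certain. It does not rescue the rule: that reading conditions on the future and overstates Kaplan-Meier even when the risks are independent.

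**It could be a cause-specific analysis of the first hospitalization of any cause.** That gives the same data as the literal reading, but it is not the variable that the section names.

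**A specific section may override a general one.** It may, so the departure from 3.1.2 is not an error in itself. The difficulty is that no reason is given and nothing in the SAP supplies one. The protocol is not at hand. If it made such an admission end treatment, 3.1.2 would already censor at discontinuation.

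**A reader might also infer a conflict over the period.** Section 3.4.1.10 says "Period refers to the whole study period", which by Section 1.2 "refers to both on-treatment and off-treatment (post-treatment follow-up) periods", while the censoring is at last dose. The documents do not support making this a defect. Sections 4.2.4.1 and 4.2.4.3 both pair that phrase with on-treatment analysis, where it evidently means not limited to the first year. The same bullet appears in most of Section 3.4.1, so changing it here alone would create an inconsistency.

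**The consequence is small.** This stands. Every admission rate, the frailty and any treatment effect on non-COPD admissions are assumed, and the larger hazard-ratio shifts need all of them together.

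**Conclusion.** The censoring rule is unsupported by the SAP and should be removed, as a minor correction. Under the literal reading it costs events and precision, and it understates Kaplan-Meier if the two risks are positively correlated. Under the restricted reading it loses no event but overstates Kaplan-Meier. The direction of these errors follows from the wording; their size rests on the assumed rates.

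A reader might conclude that the treatment comparison is seriously biased or that a main result is at risk. The documents do not support that. The hazard ratio barely moves unless treatment also changes non-COPD admissions. The endpoint is an additional efficacy variable outside the testing sequence of Section 4.2.4. COPD hospitalization is tested formally as a first-year rate, which does not use this rule. The primary efficacy, secondary efficacy and MACE conclusions are unaffected.

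**What to change.** Replace both censoring sentences of Section 3.4.1.10 with the approach of 3.4.1.6: *patients without a COPD hospitalization are censored under the general rules of Section 3.1.2*. For the on-treatment analysis in 4.2.4.3 this means treatment discontinuation or end of treatment, with deaths as censoring events and no censoring at a non-COPD hospitalization.

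Deleting only the last sentence is not enough. The sentence before it covers only patients with no hospitalization of any kind, so those with just a non-COPD admission would have no rule.

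The study-closure clause should go too. A patient who completes 36 months has not discontinued treatment and would be carried to closure, although 3.1.1 plans only a phone contact 15 days after the end-of-treatment visit and 3.1.2 censors completers at that visit in the on-study analysis. If closure came at year 4 (an assumption), the first patient enrolled would be credited with 4 - 3 = 1 year of unobserved event-free time.

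The cost is a wording change in one SAP section and the matching derivation. No new data are needed.
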